## 2.10 Analysis of Baseline Demographics and Procedural Characteristics

Demographic and baseline characteristics, procedural characteristics, lesion characteristics will be compared between the two treatment groups in each BIOFLOW-V analysis population (ITT, modified ITT and PP) and the BIOFLOW- II and -IV Bayesian analysis population by treatment. Demographic, medical history and other clinically relevant baseline variables will be summarized by treatment using descriptive statistics (i.e. number of observations available, mean, standard deviation, minimum, and maximum for continuous variables and counts and percentages for qualitative variables). Treatment difference on dichotomous variables will be evaluated using Fisher's exact tests. Categorical variables will be compared between treatments using the Cochran-Mantel-Haenszel (CMH) Modified Ridit Scores, i.e. CMH of general association for nominal variables and CMH of row mean score for ordinal variables.

Continuous variables will be compared between treatments using two-sample t-tests.

## 2.11 Subgroup Analysis

Subgroups for primary endpoint (TLF at 12-Month) using Bayesian analysis for the BIOFLOW-V study include:

---

 van Elteren, P.H. (1960), "On the Combination of Independent Two-Sample Tests of Wilcoxon," Bulletin of the International Statistical Institute, 37, 351-361.

- 1) Reference vessel diameter  $\leq 2.75$  mm/  $> 2.75$  mm. Subjects with at least one target lesion  $\leq 2.75$  mm will be classified with the small vessel subgroup.
- 2) Subjects  $> 75$  years of age/subjects  $\leq 75$  years of age.
- 3) Women/men.
- 4) Subjects with diabetes/subjects without diabetes.
- 5) Lesion length  $> 26$  mm and  $\leq 26$  mm in length
- 6) Single stents versus overlapping stents for lesion lengths  $> 26$  mm
- 7) Subjects with baseline ACS versus without ACS.

ACS will be defined as:

Subjects with unstable angina or Braunwald Class IIB or any elevated cardiac enzymes at baseline.

Treatment group difference (Orsiro minus Xience) in the primary endpoint rate and the two-sided 95% credible interval of the difference will be presented within each subgroup. Only BIOFLOW-V data will be included in these analyses. A test of interaction on the primary endpoint will be performed to formally assess heterogeneity of treatment effect on the primary endpoint across subgroups in the same manner that will be used the assessment of region heterogeneity discussed above. The purpose of this analysis is not to formally assess non-inferiority within each subgroup, but simply to assess consistency of results across the various subgroups. Subjects with an event or with appropriate follow-up will be included in this analysis.

## 2.12 Adverse Event Analysis

Adverse events collected in the BIOFLOW-V data will be summarized using descriptive statistics

- Site-reported U(S)ADE presented by system organ class and preferred term
- Site-reported AE presented by system organ class and preferred term
- Site-reported SAE presented by system organ class and preferred term
- Site-reported device-related AEs presented by system organ class and preferred term

Posterior probability calculations comparing the treatment groups will only be presented for AEs and SAEs whose frequency exceeds 10. If  $p_O$  and  $p_X$  are the probability of the AE with the Orsiro and Xience stents, we will report the posterior distribution that  $p_O > p_X$ , that is, the posterior probability that the probability of the AE is larger with the Orsiro stent than with Xience stent. Non-informative independent priors Beta (0.1, 0.1) will be assumed on  $p_O$  and  $p_X$ , respectively.

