8.13. Adverse Event Analysis

Only AEs whose frequency exceeds 10 will be compared between the two groups. For those AEs, if p_o and p_x are the probability of the AE with the Orsiro and Xience stents, we will report the posterior distribution that $p_o > p_x$, that is, the posterior probability that the probability of the AE is larger with the Orsiro stent than with Xience stent. Non-informative independent priors Beta (0.1,0.1) will be assumed on p_o and p_x , respectively.

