### 1.2 Trial Design

BIOFLOW-V is a prospective, multicenter, randomized, controlled trial combining data on the randomized subjects with data from two historical studies by employing a Bayesian approach.

Subjects with coronary artery disease (CAD) that qualify for percutaneous coronary intervention (PCI) with stenting will be screened per the protocol inclusion and exclusion criteria to achieve a total of at least 1,334 and up to 1,400 randomized subjects. Eligible subjects will be randomized, stratified by study center, in a 2:1 ratio to undergo percutaneous coronary revascularization with either the Orsiro Sirolimus Eluting Stent System (treatment group, at least 889 and up to 933 subjects) or the Xience Everolimus Eluting Stent System (control group, at least 445 and up to 467 subjects). The study will include up to 100 clinical sites in the United States and 50 clinical sites outside of the United States.

BIOFLOW-V randomized subjects will be combined with historical Orsiro, Xience Prime™ and Xience Xpedition™ randomized subjects from the BIOFLOW-II and BIOFLOW-IV trials by employing a Bayesian statistical approach. Only subjects that meet all clinical and angiographic eligibility criteria of the BIOFLOW-V trial will be included in the analysis.

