### 2.5 Sample Size Determination

The BIOFLOW-V trial will assess non-inferiority of the 12-month TLF rate for the Orsiro stent vs. TLF rate in subjects treated with the Xience stent. The null hypothesis  $H_0$  is that the Orsiro stent will have a primary endpoint (TLF) rate equal to or exceeding that of the Xience group by the non-inferiority margin or more. The alternative hypothesis  $H_A$  is that the Orsiro stent will have TLF rate less than the Xience group rate plus the non-inferiority margin. Specifically:

$$\begin{aligned} H_0: \pi_X^V - \pi_O^V &\leq -\delta \\ H_A: \pi_X^V - \pi_O^V &> -\delta \end{aligned}$$

Where  $\pi_O^V$  is the true 12-month TLF rate for the Orsiro stent,  $\pi_X^V$  is the true 12-month TLF rate for the Xience arm, and  $\delta$  is the non-inferiority margin.

The assumptions for this analysis are:

- True 12-month TLF rate is 7.0% in both treatment groups ( $\pi_X^V = \pi_O^V$ ).
- Power is 89%.
- 3.85% is the absolute non-inferiority margin (55% relative non-inferiority margin).
- Discount the results of the BIOFLOW-IV data by 20% and BIOFLOW-II data by 30%.
- Standard deviation of the bias terms between the odds of BIOFLOW-II TLF 12-month rates and odds of BIOFLOW-V 12-month rates is 0.3.
- Standard deviation of the bias terms between the odds of BIOFLOW-IV TLF 12-month rates and odds of BIOFLOW-V 12-month rates is 0.3.
- Non-inferiority assessment will be assessed using the posterior probability of the alternative hypothesis as specified above, where  $\pi^* = 0.975$

Rejection of the null hypothesis signifies that the Orsiro stent is not inferior to the Xience stent with regards to 12-month TLF. A total of 1,200 subjects (800 in the Orsiro group and 400 in the Xience group) will have 89.6% power to reject the above null hypothesis in favor of the alternative under the stated assumptions. To account for loss to follow-up (expected to be approximately 10%), a total of 1,334 subjects will need to be randomized. The one-sided type I error estimates are 4.0%, 3.3%, and 4.2% if the actual odds for the 12-month TLF rate of event in the Xience group of the BIOFLOW-IV study are the same, 10% lower and 10% higher when compared with the odds for the 12-month TLF rate of event in the Xience group of the BIOFLOW-V study.

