## 2.9 Analysis of Secondary Endpoints

The secondary endpoints in the BIOFLOW-V study will be analyzed using frequentist methods. For each endpoint, the proportion and sample size will be calculated and reported for the Xience group and for the Orsiro group. Fisher’s exact test will be used to test the difference between the groups. Analyses of secondary endpoints will be carried out on the ITT, Modified ITT and PP analysis sets for BIOFLOW-V. However, there will be no direct imputation of missing data. Secondary Endpoints include the following measures:

- 1) Device success
- 2) Lesion success
- 3) Procedure success

BIOFLOW-V will utilize the percent residual stenosis, as assessed by the investigator for the primary analysis measure of the % residual stenosis for evaluating angiographic success for the aforementioned secondary endpoints. If investigator assessment of residual stenosis is not available, the in stent final % diameter stenosis as assessed by QCA will be used. MACE included in the procedure success will use the primary analysis definitions.

Treatment group difference (Orsiro minus Xience) in the success rates and the two-sided 95% confidence intervals of the difference will be presented.

The following secondary clinical endpoints will be evaluated prior to discharge, at 1-, 6- and 12-months and annually:

- 4) Death
- 5) Protocol-defined MI
- 6) Cardiac death or protocol-defined MI
- 7) MACE and individual MACE components
- 8) TLF and individual TLF components
- 9) TVF and individual TVF components
- 10) Stent thrombosis according to ARC criteria

Included in the analysis, will be subjects experiencing the event or who have adequate follow-up (e.g., at least 23 days for 1-month time point, at least 166 days for the 6-month time point, and at least 330 days for the 12-month time point).

All the re-adjudicated clinical endpoints in BIOFLOW-II and BIOFLOW-IV will be summarized by study and treatment group.

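### The frequency-above-10 filter in SAP 2.12 withholds the between-arm comparison for rare site-reported SAEs that are not study endpoints, even at a 10-to-0 split against Orsiro

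*SAP*

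**What the plan says.** SAP 2.12 limits its comparison of adverse events between arms: "Posterior probability calculations comparing the treatment groups will only be presented for AEs and SAEs whose frequency exceeds 10". Protocol 8.13 has the same limit for AEs without naming SAEs separately: "Only AEs whose frequency exceeds 10 will be compared between the two groups". Neither gives a reason for 10, and neither exempts serious events, device-related events or U(S)ADEs.

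The quantity reported above the limit is the posterior probability that the event is more likely with Orsiro than with Xience. On the prior, the SAP says: "Non-informative independent priors Beta (0.1, 0.1) will be assumed on" the two event probabilities.

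Below the limit, events are still listed. SAP 2.12 plans descriptive tables with no cut-off, including: "Site-reported SAE presented by system organ class and preferred term". The same applies to AEs, device-related AEs and U(S)ADEs.

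SAP 2.9 handles clinical endpoints separately. For death, protocol-defined MI, cardiac death or MI, MACE, TLF, TVF and ARC stent thrombosis, Fisher's "exact test will be used to test the difference between the groups", with no minimum count.

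**The concern.** The filter selects on the total number of events, not on seriousness or imbalance. A common, evenly spread event is compared; a rare serious one is not, however lopsided. With 1,334 to 1,400 randomized subjects, a pooled count of 10 is an observed incidence of 10/1,334 = 0.75% to 10/1,400 = 0.71%. Protocol 13.1 lists serious complications that could fall there and are not secondary endpoints: perforation, tamponade, stent embolization, stent dislodgement, stroke, and hemorrhage requiring transfusion. Tabulating by preferred term divides the counts further.

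The allocation is 2:1, so raw counts are awkward to read: 6 against 3 is balanced. The trial objective includes safety, and for these terms the clinical study report would give counts without any comparison.

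**Working it through.** **Inputs.** Orsiro arm (SAP 1.2): "treatment group, at least 889 and up to 933 subjects". Xience arm (SAP 1.2): "control group, at least 445 and up to 467 subjects". Prior Beta(0.1, 0.1) in each arm and threshold above 10 (SAP 2.12). The threshold has no stated derivation to reproduce. The denominators do: SAP 2.5 says "To account for loss to follow-up (expected to be approximately 10%), a total of 1,334 subjects will need to be randomized", and 1,200/(1 − 0.10) = 1,334 (rounded up). With the optional increase in Protocol 8.5, 1,260/(1 − 0.10) = 1,400.

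**Reading of frequency.** I take it as the number of subjects with the event, pooled over arms. That is an assumption. A per-arm count would also exclude 10-0. An event count would admit 10 subjects who had 11 or more events between them. A percentage would exclude far more.

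**Step 1: individual splits.** With x events in n subjects, each arm's posterior is Beta(c + x, c + n − x), where c = 0.1 is the SAP prior and c = 0.5 the alternative. The reported quantity is P(p_O > p_X) for independent posteriors. At 933/467:

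| Orsiro-Xience | Total | Shown under the filter? | c = 0.1 | c = 0.5 | Fisher, two-sided |
|---|---|---|---|---|---|
| 10-0 | 10 | No | 0.9995 | 0.996 | 0.036 |
| 9-1 | 10 | No | 0.970 | 0.953 | 0.18 |
| 6-0 | 6 | No | 0.996 | 0.976 | 0.19 |
| 5-0 | 5 | No | 0.994 | 0.96 | 0.18 |
| 3-0 | 3 | No | 0.979 | 0.897 | 0.56 |
| 7-4 | 11 | Yes | 0.43 | 0.40 | 1.00 |

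The 10-0 split is 10/933 = 1.07% against 0%. If the true rates are equal, the chance that all of 10 events fall on Orsiro is (2/3)^10 = 1.7%. At 889/445 the 10-0 posterior under the SAP prior is also 0.9995.

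**Step 2: how often the filter hides an imbalance.** For true rates r_O and r_X, sum Bin(x_O; 933, r_O) × Bin(x_X; 467, r_X) over all pairs with x_O + x_X ≤ 10, then over those pairs that also meet the criterion. The rates are illustrative five-fold excesses and are not in the documents.

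| True rates | Total ≤ 10 | Hidden posterior > 0.975, c = 0.1 | Same, c = 0.5 | Hidden Fisher p < 0.05 |
|---|---|---|---|---|
| 1.0% / 0.2% | 55% | 26% | 22% | 10% |
| 0.75% / 0.15% | 85% | 43% | 30% | 9% |
| 0.5% / 0.1% | 98% | 52% | 20% | 2.5% |

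**Step 3: false flags with no filter.** With identical true rates in both arms, the chance that the posterior exceeds 0.975 is:

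| Common rate | c = 0.1 | c = 0.5 |
|---|---|---|
| 0.2% | 11.3% | 0.5% |
| 0.3% | 13.1% | 1.6% |
| 0.5% | 8.6% | 3.3% |

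Under the SAP prior this is about 9-13%, so removing the filter without changing the prior would produce many spurious flags.

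**The case against.** A reader might infer that rare serious events get no treatment comparison at all. The documents do not support that. SAP 2.9 compares death, MI, MACE, TLF, TVF and stent thrombosis by Fisher's exact test at any count, on CEC-adjudicated data. These are the serious events most central to a stent trial, and stent thrombosis is the device risk that the protocol itself stresses.

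Other safeguards exist. All SAEs are tabulated, and the DMC reviews safety unblinded (Protocol 11.2). SAP 2.10 compares procedural characteristics between arms with no count threshold. It does not list the variables, so some procedural complications may be covered there; stroke or late bleeding would not be expected among them. DMC review during the trial does not supply a comparison in the final report.

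The filter can also be defended as a guard against chance flags over many sparse terms. That has force under Beta(0.1, 0.1), which exceeds 0.975 at only 3-0. It is equally a reason to change the prior, and it does not explain why adjudicated endpoints are tested at any count while other SAEs are not. The size also depends on the yardstick: at 0.5%/0.1%, 52% of trials under the SAP prior becomes 20% under Beta(0.5, 0.5) and 2.5% under Fisher's test. Finally, no success criterion depends on these probabilities.

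**Conclusion.** The point holds for a limited set of events: site-reported SAEs that are not study endpoints, together with device-related AEs and U(S)ADEs. For these, SAP 2.12 withholds the only comparison the plan names whenever the frequency is 10 or fewer, including a 10-0 split that is notable under either prior and under Fisher's test, while a balanced 7-4 split is shown.

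A fair statement of size is 22%, 30% and 20% of trials with a hidden posterior above 0.975, under Beta(0.5, 0.5). The SAP-prior figures of 26%, 43% and 52% should not be read as the true loss, because that prior overreacts to zero cells. All these figures assume a pooled subject count, arms of 933 and 467, and a five-fold true excess. The primary analysis and the adjudicated safety endpoints are untouched. This is an inexpensive improvement to safety reporting and not a flaw that threatens the trial's conclusion.

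**What to change.** Revise SAP 2.12 before database lock:

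1. Define frequency as the number of subjects with the event, pooled across arms.
2. Keep the above-10 filter for non-serious AEs only.
3. For SAEs, device-related AEs and U(S)ADEs, present the between-arm comparison at any count. Use either the risk difference (Orsiro minus Xience) with an exact interval or the posterior probability under Beta(0.5, 0.5). Do not remove the filter while retaining Beta(0.1, 0.1) for these sparse tables.
4. Label these comparisons as unadjusted for multiplicity.

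Protocol 8.13 carries the same filter and prior, so it should be aligned, or the SAP should record the departure as SAP 2.8 does for the time-to-event model. The cost is a few sentences and more table rows. The real downside is that more chance imbalances will be displayed and will need clinical interpretation.

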## 2.13 Additional Analyses

The following data collected in BIOFLOW-V will be summarized using descriptive statistics

- Subject enrollment by site and compliance by follow-up visits
- Baseline cardiovascular and antidiabetic medication
- Dual Antiplatelet Therapy Compliance (DAPT) at Visit Intervals
- Subjects with missing adequate post-procedure cardiac enzymes will be presented by discharge time.

- Analysis on subjects with missing cardiac enzymes, including the baseline characteristics for subjects with missing adequate pre-procedure and missing post-procedure cardiac enzymes, respectively. This analysis will also be performed in BIOFLOW-II and -IV.
- Primary endpoint analyzed removing the peri-procedural MIs.

[figure not shown]
### **3 BIOFLOW-II and BIOFLOW-IV DATA for ANALYSIS**

Data from BIOFLOW-II and BIOFLOW-IV studies will be uploaded by Biotronik as zip files on a Baim internal FTP. Baim's IT Department will copy the zip files to standard network folders, one for each protocol, where Baim's clinical data is stored, per guideline GIT.011. Zip files will be opened using WinZip software and their contents will be extracted to the same subfolders. Baim's Project Management representative will be notified once the download and extract of both protocols' zip files. In creating the analysis data, data for the BIOFLOW-II and BIOFLOW-IV studies will be processed using the same scripts used for data processing for BIOFLOW-V to assure a uniform definition of the analysis data across the 3 studies. The resulting data for the 3 studies will be merged into a single dataset (analysis data set, ADS), which will follow a separate document (ADS specification) containing all the specific data mappings across BIOFLOW-II, BIOFLOW-IV and BIOFLOW-V. The detailed schematic of the steps, qualify control (QC) associated with the data merge process are outlined in the data merge flow diagram below.

Combined analysis (of II, IV and V using Bayesian statistics) will be performed for the TLF (primary endpoint) and its components; combined analysis will not be performed for other secondary endpoints.

Baim Data Merge Flow – BIOFLOW-II, BIOFLOW-IV, BIOFLOW-V

Revised April 26, 2017

#### **4. Addendum**

Bayesian superiority analysis is performed if the primary hypothesis of non-inferiority is met. The superiority hypothesis is evaluated by computing the posterior probability of the superiority alternative hypothesis. This posterior probability is compared against the same threshold pre-specified for the non-inferiority test (97.5%).
